In the Japanese Phase III clinical study (JP321), in which favipiravir was administered at 1,800/800 mg BID, which is the same dosage as in this clinical study, in repeated doses for 10 days in patients with severe fever with thrombocytopenia syndrome (SFTS), three AEs (SFTS) that resulted in death occurred in three patients and six other SAEs (liver function test increased, Factor XIII deficiency, sepsis, myocarditis, seizure and respiratory arrest, one event each) in five patients. All these AEs, except for liver function test increased and seizure, were judged by the Principal Investigator to be unrelated to the study drug. The incidence of AEs was 86.7% (26/30 patients, 116 events). Adverse events with an incidence of $\geq 10\%$ were hyperglycemia and hyperuricemia each in 23.3% (7/30 patients), insomnia and blood uric acid increased each in 20.0% (6/30 patients), constipation and rash each in 16.7% (5/30 patients), back pain in 13.3% (4/30 patients), oral candidiasis, SFTS, hypertriglyceridemia and pneumonia aspiration each in 10.0% (3/30 patients). The incidence of AEs for which a causal relationship with the study drug could not be ruled out was 70.0% (21/30 patients, 40 events). Adverse events with an incidence of $\geq 10\%$ were hyperuricemia in 23.3% (7/30 patients), blood uric acid increased in 20.0% (6/30 patients), and hypertriglyceridemia in 10.0% (3/30 patients).

In a prospective, randomized, controlled, open-label study¹³ conducted on adult patients with COVID-19, 116 patients received Favipiravir (twice daily) and 120 patients received Umifenovir (thrice daily) plus standard care. Favipiravir was started with 1600 mg on the first day followed

Study code: NV-05-983-2020
Protocol No.: CVD-04-CD-001
Sponsor name: [name], Limited
Clinical Study Protocol

by 600 mg for the following days upto a maximum of 10 days. In the comparator arm Umifenovir was given at 200 mg combined with standard care for 7 days. On Day 7, the clinical recovery rate in Favipiravir group was 71/116 and Umifenovir group was 62/120. There was no significant difference between the 2 groups. In Favipiravir group there was a significant improvement with respect to relief for fever and cough. But there was an increase in serum uric acid observed in 16 patients receiving Favipiravir.

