1.3 Risks and Benefits for Study Patients

Many medicinal treatments for COVID-19 disease are being administered off-label, or in the experimental setting. In this study, we are evaluating one such potential treatment, favipiravir, which has demonstrated some indirect and direct evidence of efficacy in the management of COVID-19 patients over and above the standard of care in accordance with the institutional guidelines.

Patients will have clinical assessments, assays for detection of the SARS-CoV-2, other clinical laboratory evaluations and chest imaging performed, at more than one time points during the course of this study, at no cost to them, and may benefit from close medical oversight in the course of safety assessments in the trial. Finally, they would have altruistic satisfaction of having directly contributed to medical scientific research against an infectious disease that has emerged as a major current challenge to the human race, as well their immediate personal health.

The risks to the study patients from study participation are that, they could possibly experience one or more adverse effects from any medications used as and from favipiravir such as blood uric acid increased, diarrhea, neutrophil count decreased, aspartate aminotransferase (AST) increased, alanine aminotransferase (ALT) increased.

Serious adverse events reported in subjects taking this drug are hepatic function abnormality, hematochezia, colitis, seizure and acute kidney injury. It is not known if all are attributable favipiravir administration.

The clinically significant adverse reactions of similar (anti-influenza) drugs requiring particular attention include shock, anaphylaxis, pneumonia, hepatitis fulminant, hepatic function disorder, jaundice, TEN, oculomucocutaneous syndrome (Stevens-Johnson syndrome), acute renal failure, neurological and psychiatric symptoms (consciousness disturbed, abnormal behavior, delirium, hallucination, delusion, convulsion, etc.), and colitis hemorrhagic.

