3.1.6.2 Study Treatment Discontinuation

3.1.6.2.1 Study treatment discontinuation criteria

When a patient meets any of the following criteria, the Principal Investigator or a Sub-Investigator will discontinue administering the study drug to that patient.

- a. The patient requests withdrawal from the clinical study
- b. If the patient requests discontinuation of administration of the study drug
- c. The patient died
- d. The patient is lost to follow-up
- e. If an AE occurs and the Principal Investigator or a medically qualified Sub-Investigator judges that continuing with the administration of the study drug would not be in the interest of patient's safety or well-being
- f. If a patient experiences a serious adverse event assessed by Investigator and/or Medical Monitor to be reasonably causally related to the IMP (FPV/Placebo)
- g. If a patient becomes pregnant while receiving IMP (FPV/Placebo)
- h. If patient's serum uric acid or hepatic transaminases levels are assessed as Grade 3 severity by National Institutes of Health (NIH) National Cancer Institute (NCI) Common Terminology Criteria for Adverse Events (CTCAE)²³, at any timepoint during the treatment period
- i. If a patient is otherwise deemed ineligible to continue in the study by the Principal Investigator or a Sub-Investigator
- j. Upon request by the CRO or Sponsor Medical Monitor (with appropriate justification)

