9.1.1.2 Serious Adverse Event (SAE)

A serious adverse event is defined as any untoward medical occurrence that at any dose:

- Results in death,

Study code: NV-05-983-2020
 Protocol No.: CVD-04-CD-001
 Sponsor name: [name], Limited
 Clinical Study Protocol

- Is life-threatening,
- Requires inpatient hospitalization or prolongation of existing hospitalization,
- Results in persistent or significant disability/incapacity,
- Is a congenital anomaly/birth defect, or
- Is an important medical event.

Note: *The term “life-threatening” in the definition of “serious” refers to an event in which the patient was at risk of death at the time of the event; it does not refer to an event which hypothetically might have caused death if it were more severe.*

Medical and scientific judgment should be exercised in deciding whether expedited reporting is appropriate in other situation, such as important medical events that may not be immediately life-threatening or result in death or hospitalization but may jeopardize the patient's safety or may require intervention to prevent one of the other outcomes listed in the definition above. Examples include allergic bronchospasm, convulsions, and blood dyscrasias or development of drug dependency or drug abuse.

Note:

- *A procedure is not an AE or SAE, but the reason for the procedure may be an AE.*
- *Pre-planned surgeries or hospitalizations for pre-existing conditions which do not worsen in severity are not SAEs.*
- *Routine treatment or monitoring of the studied indication not associated with deterioration in condition should not be considered as SAE. For example, in the patient population for the current study, administration of supplemental oxygen should not in itself be considered as SAE, unless it is associated with a significant deterioration in subject's condition (such as development of ARDS and/or respiratory failure requiring invasive mechanical ventilation).*
- *. Hospitalization or prolongation of hospitalization for technical, practical, or social reasons, in absence of an AE should not be considered as SAE.*
- *Abnormal clinically significant laboratory values should not be reported as SAEs, unless they lead to prolongation of hospitalization on their own, while the underlying disease condition merited a discharge from the hospital.*

Adverse Event Reporting Period

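### The laboratory note in Protocol 9.1.1.2 contradicts the seriousness criteria above it, so isolated serious laboratory abnormalities could miss SAE reporting

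*Protocol*

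**What the plan says.** Protocol 9.1.1.2 makes any untoward medical occurrence an SAE if it meets any one of six criteria. Three matter here: "Is life-threatening", "Requires inpatient hospitalization or prolongation of existing hospitalization" and "Is an important medical event". The list makes no exception for laboratory findings, and the examples given for the last of the three include blood dyscrasias.

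The last note under the list narrows this for laboratory results: "Abnormal clinically significant laboratory values should not be reported as SAEs, unless they lead to prolongation of hospitalization on their own". The same sentence adds a second condition to its exception: "while the underlying disease condition merited a discharge from the hospital".

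Two later sub-headings of 9.1.1.2 also bear on the point:
- *Hospitalization, Prolonged Hospitalization or Surgery* says that an AE leading to admission or to a longer stay is to be reported as an SAE.
- *Abnormal Laboratory Values* makes a clinically significant result an AE if a repeat test does not refute it, if it points to disease or organ toxicity (the underlying condition is then what is recorded), or if it needs active management.

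Section 9.1 separately requires every post-baseline result that the investigator considers clinically significant to go on the AE page.

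**The concern.** The note does more than say that an abnormal value is not serious in itself. It states one circumstance in which a laboratory value may be an SAE and excludes the rest, including circumstances that the list above it makes serious.

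Serious status controls four things: the report to the CRO within 24 hours (Protocol 9.2), SUSAR handling (9.2.1), study-treatment discontinuation criterion (f) for related SAEs (3.1.6.2.1), and the SAE tables (SAP 10.7.1). A value-only event that a site leaves out because of the note misses all four. Sites that follow the list and sites that follow the note will also classify the same event differently.

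**Working it through.** The plan states no figure on this point, so the check sets the rules side by side.

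**Step 1. What the note leaves of each criterion for a laboratory value**

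| Criterion in 9.1.1.2 | Under the list | Under the note |
|---|---|---|
| Life-threatening | SAE | Barred |
| New inpatient admission | SAE | Barred |
| Prolongation of an existing stay | SAE | SAE only if the value alone prolongs the stay and the disease already merited discharge |
| Important medical event | SAE | Barred |

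The other three criteria (death, disability, congenital anomaly) are also outside the exception, but in practice they would attach to a condition rather than to a value. The note therefore keeps part of one criterion out of six.

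**Step 2. When the exception can apply**

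Inclusion criteria 3 and 4 (Protocol 4.1.1) require patients to be in hospital and on supplemental oxygen at entry.
- While the disease still needs the stay, discharge is not merited and the exception fails.
- After discharge, a patient may still be on study drug at home, with blood drawn there for haematology and biochemistry at the Day 10 assessment (6.3.1.4). There is no stay to prolong, so the exception fails again.
- It fits only the period when a patient is otherwise ready to leave.

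**Step 3. Five cases**

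1. Inpatient on oxygen with a value that puts the patient at risk of death at that time: serious under the list, barred by the note.
2. Discharged patient readmitted because of a Day 10 value: an SAE under the list and under the hospitalisation sub-heading, barred by the note.
3. Discharged patient with a value judged an important medical event, not admitted: serious under the list, barred by the note.
4. Patient ready for discharge and kept in hospital only because of the value: an SAE under every rule.
5. Value that suggests organ toxicity, with the condition recorded as the AE: the condition is judged on all six criteria and the note does not reach it.

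The rules conflict in cases 1 to 3 and agree in cases 4 and 5.

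**Step 4. Does the protocol expect value-only AEs?**

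Yes. Two of the three conditions under *Abnormal Laboratory Values* (not refuted on repeat; needs active management) create an AE without naming a condition.

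**Step 5. Is there a precedent?**

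Protocol 1.1.4 describes a study of 30 patients with SFTS, a different disease, at the same dosage for 10 days. Apart from three fatal events it reports "six other SAEs (liver function test increased, Factor XIII deficiency, sepsis, myocarditis, seizure and respiratory arrest, one event each) in five patients". All but two of these, the raised liver function test and the seizure, were judged unrelated to study drug. So 1 of the 6 was a laboratory term, and it was 1 of the 2 not judged unrelated. Under the present note an event like it would be an SAE only if it met the narrow exception or was recorded as a condition.

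**The case against.** The strongest case on the other side is that little is lost, and much of it stands.

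- **Conditions stay reportable.** A reader might infer that the note takes the drug's named hepatic and renal signals out of SAE reporting. The documents do not support that. Protocol 1.3 says: "Serious adverse events reported in subjects taking this drug are hepatic function abnormality, hematochezia, colitis, seizure and acute kidney injury". The hepatic and renal items are worded as conditions, and the note covers values. A value need only suggest organ toxicity for the underlying condition to be recorded instead. No renal laboratory-term SAE appears anywhere in the documents.
- **The data are not lost.** Clinically significant values remain on the AE page. SAP 10.7.1 tabulates TEAEs by severity and relationship, and SAP 10.7.2 tabulates abnormal and clinically significant laboratory results by treatment group.
- **There is another discontinuation route.** Criterion (h) in 3.1.6.2.1 acts on Grade 3 uric acid or transaminases whatever the SAE status.
- **The note has a sensible purpose.** Protocol 1 lists raised ALT, AST and creatinine as common in COVID-19 itself, and many asymptomatic elevations would meet no seriousness criterion.
- **A patient count is not supportable.** One might scale the earlier study: 1/30 × 390 = 13 favipiravir patients. The exact 95% interval for 1/30 is about 0.1% to 17%, or roughly 0.3 to 67 of 390. The calculation also assumes that no such event would meet the exception or be recorded as a condition, and 1.1.4 does not say why that one event was serious.
- **A direction of bias is not shown.** One might infer that the missing events fall mainly on favipiravir and hide harm. Laboratory abnormalities caused by the disease would arise in both blinded arms.

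None of this removes the contradiction. AE tables and laboratory tables do not trigger a 24-hour report. Criterion (h) covers two kinds of test and is not a reporting route. The underlying-condition route does not help when only the value is recorded.

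**Conclusion.** The concern holds as a contradiction in the safety-reporting rules. The laboratory note in 9.1.1.2 cannot be reconciled with the life-threatening, new-hospitalisation and important-medical-event criteria in the same section, nor with its rule on AEs that lead to hospitalisation. A site that follows the note would leave some serious events out of SAE reporting.

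What is exposed is limited to serious laboratory abnormalities recorded with no underlying condition, and the documented example is hepatic. Those events could miss the 24-hour report, SUSAR handling, criterion (f) and the SAE tables, while remaining in the AE and laboratory data. This rests on sites applying the note as written. How many patients would be affected, and whether the between-arm SAE comparison would shift in either direction, cannot be established from the documents. The point needs correcting because it governs expedited reporting, whatever the count.

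**What to change.** Reconcile the note with the six criteria and with the hospitalisation rule in the same section by replacing it with:

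> A laboratory abnormality is not an SAE merely because it is abnormal or clinically significant; it is reported as an SAE whenever it meets any seriousness criterion in 9.1.1.2.

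This keeps the note's legitimate aim and restores every criterion. The other notes can stay as they are. The cost is one sentence in the protocol, the same sentence in any SAE completion guidance, and a few more SAE forms. No new assessment is needed.

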9.1.1.3 AE Severity

The intensity or severity of AEs will be done by two methods:

- a. The severity of the respective AEs will be graded using the NIH NCI CTCAE Version 5.0. Published: November 27, 2017²³.
- b. Additionally, the following definitions should be used to assess severity of AEs:
 - Grade 1 Mild: asymptomatic or mild symptoms; clinical or diagnostic observations only; intervention not indicated.
 - Grade 2 Moderate: minimal, local or non-invasive intervention indicated; limiting age appropriate instrumental Activities of Daily Living (ADL)*.
 - Grade 3 Severe or medically significant but not immediately life-threatening: hospitalization or prolongation of hospitalization indicated; disabling; limiting self care ADL**.
 - Grade 4: Life-threatening consequences; urgent intervention indicated.
 - Grade 5: Death related to AE.

Activities of Daily Living (ADL)

*Instrumental ADL refer to preparing meals, shopping for groceries or clothes, using the telephone, managing money, etc.

Study code: NV-05-983-2020
 Protocol No.: CVD-04-CD-001
 Sponsor name: [name], Limited
 Clinical Study Protocol

**Self care ADL refer to bathing, dressing and undressing, feeding self, using the toilet, taking medications, and not bedridden.

9.1.1.4 Causality Assessment

The relationship between an AE and the study drugs will be determined by the Investigator on the basis of his/her medical/ pharmacological knowledge and clinical judgment and the following definitions:

- **Not Related:** The event is clearly due to extraneous causes (e.g., diseases, environment, etc.) (specify if known) or, the event is most probably produced by other factors such as the patient's clinical state, therapeutic interventions, or concomitant therapy and does not follow a known response pattern to the study product.
- **Possibly Related:** The event is temporally related to study product use but can be explained by another etiology. Information on the effect of study product withdrawal may be lacking.
- **Probably Related:** The event is temporally related to study product use and is consistent with known effects of the study product and/or improves upon withdrawal of the study product.
- **Definitely Related:** The event follows a reasonable temporal sequence from the time of study product administration and/or follows a known response pattern to the study product, and could not have been produced by other factors such as the patient's clinical state, therapeutic intervention, or concomitant therapy, and either occurs immediately following study product administration or improves on stopping the product, or there is a positive reaction at the application site

9.1.1.5 Action Taken Regarding the Study Product

The action taken regarding the study product will be categorized as below;

Grading	Category	Definition
1	None	No change in study drug dosage was made
2	Discontinued Permanently	The study product was permanently stopped
3	Reduced	The dosage of study product was reduced
4	Interrupted	The study product was temporarily stopped.
5	Increased	The study product dosage was increased

9.1.1.6 Adverse Event Outcome

The outcome of the AE will be categorized as below;

Study code: NV-05-983-2020
 Protocol No.: CVD-04-CD-001
 Sponsor name: [name], Limited
 Clinical Study Protocol

Grading	Category	Definition
1	Recovered/Resolved	The patient fully recovered from the AE with no residual effect observed
2	Recovered/Resolved with Sequelae	The residual effects of the AE are still present and observable. Identify sequelae/residual effects
3	Not Recovered/Not Resolved	The AE itself is still present and observable
4	Fatal	The AE resulted in death of the patient or contributed significantly to it
5	Unknown	The outcome of the AE in the patient is not known or cannot be determined.

9.1.1.7 Other Action Taken for Event

The other action taken for the AE will be categorized as below;

Grading	Category	Definition
1	None	No treatment was required
2	Medication required	Prescription and/or OTC medication was required to treat the AE
3	Hospitalization or prolongation of hospitalization required	Hospitalization was required or prolonged due to the AE, whether or not medication was required
4	Other	

9.2 Serious Adverse Event Reporting

Procedure for Investigator

All serious adverse events (SAEs) should be reported immediately to the CRO (at the below mentioned e-mail address), who will relay it to Sponsor. The Investigator will report the SAEs using SAE form via email, regardless of the Investigator's determination of causality at least within 24 hours of the Investigator becoming aware of the event on dedicated SAE Reporting Form.

SAE Reporting Contact Information
[contact]

Study code: NV-05-983-2020
Protocol No.: CVD-04-CD-001
Sponsor name: [name], Limited
Clinical Study Protocol

In particular, if the SAE is fatal or life-threatening, the CRO must be notified immediately, irrespective of the extent of available AE information. This timeframe also applies to additional (follow-up) information that becomes available on previously forwarded SAE reports.

At a minimum, the Investigator must provide the following information: protocol number, site ID, patient initials, patient number and date of event initiation, event term and causality in the initial SAE form.

The Investigator is obligated to pursue and provide information to Sponsor and the responsible CRO on all SAEs in accordance with the timeframes for reporting specified above. In addition, an Investigator may be requested by Sponsor and the responsible CRO to obtain specific additional follow-up information in an expedited fashion. This information may be more detailed than that captured on eCRF. In general, this will include a description of the SAE, which should be provided in sufficient detail so as to allow for a complete medical assessment of the case and independent determination of possible causality. Information on other possible causes of the event, such as concomitant medications and illnesses must be provided. In the case of a subject death, a summary of available autopsy findings must be submitted as soon as possible to Sponsor or its designated representative.

The initial reports should be followed promptly by detailed written reports. The initial and follow-up reports should identify patients by unique code numbers assigned to the trial patients rather than by the patients' names, personal identification numbers, and/or addresses.

All SAEs will be followed until event resolution or stabilization (for chronic events), if possible, even when a subject is withdrawn from treatment. For chronic events that does not fully resolve until years later, the outcome should be reported as "resolved with sequelae" as soon as the event has stabilized or returned to baseline. Follow-up information for the SAE should be actively sought and submitted as the information becomes available.

All pre-treatment events (see [Section 9.1.1](#)) which are assessed as being serious according to the criteria listed in [Section 9.1.1.2](#) , have to be reported in the same way.

Procedure for Sponsor/CRO

Sponsor will follow expedited reporting procedures according to local and international regulations as appropriate. The Sponsor will promptly notify SAE to the applicable regulatory authorities, Ethics Committee and other investigators of the trial within applicable timelines as per the applicable regulatory requirement.

